6.2 Ensuring representativeness of the number of cases

Although deliberations regarding the number of cases are based on formal statistical principles, this is not strictly planned with respect to controlling alpha errors and statistical power. The estimate of case numbers is based on considerations such as incidence of disease, sample size in relation to the overall population and anticipated recruitment within the study period.

The number of cases of approx. 3000 corresponds to >11% of the total population with this indication, assuming that during the patient recruitment phase (October 2012 to December 2016), approx. 24,000–26,000 patients would be eligible for Afinitor[®] plus exemestane as a treatment option according to the Summary of Product Characteristics (i.e. postmenopausal women with advanced breast cancer with no symptomatic visceral metastases following a recurrence or progression after a non-steroidal aromatase inhibitor). The number of cases of up to 3000 allows sufficiently large subgroups to be formed to make a comparative analysis with respect to efficacy and quality of life between patients with high levels of physical activity and patients with low levels of physical activity.

The representativeness of the approx. 400 participating study sites is ensured by a nearly

equal regional distribution across the country. Study sites are selected exclusively on the basis of their involvement with the care of the patient collective to be studied and the interest of the site in participating in a structured case documentation and analysis project. Since no exclusion criteria are explicitly defined (i.e. all patients who fulfil the requirements for documentation can actually be documented), the representativeness of the selection within the sites is assured.

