6.1 Study sites and patients

This non-interventional, multicentre study will be conducted at approx. 400 gynaecology and oncology practices/clinics. The participating physicians will be informed of the aims and modalities of this NIS by the medical director of the NIS. The field employees of Novartis Pharma GmbH will be deployed for administrative purposes in the conduct of the NIS and will distribute all documentation materials to the participating sites.

There will be prospective documentation of the course of treatment for a total of approx. 3000 patients treated with Afinitor[®] in combination with exemestane according to routine practice and the respective Summaries of Product Characteristics. Patients may also be included in the documentation if treatment with Afinitor[®] and exemestane was started a maximum of 6 weeks before they gave their consent to participate in this NIS and they are currently receiving Afinitor[®] and exemestane. The planned observation period per patient corresponds with the duration of treatment with Afinitor[®] in combination with exemestane, but ends on completion of the observation phase. This means that the last patient will be observed for a maximum of 12 months. If the therapy with Afinitor[®] and exemestane is stopped prior to disease progression, the follow up period will be extended until time of progression / death of the patient. Observation intervals are not specified, but will be guided by current practice and the clinical symptoms of the respective patient, e.g. after approx. 2 weeks, 1 and 3 months and then at 3-month intervals (6, 9, 12 ... etc.) after the start of

treatment with Afinitor[®] and exemestane. The end of this treatment should be documented regardless of the target interval if treatment is ended before the next regularly scheduled follow-up.

The following patients are suitable for inclusion in this NIS:

- Patients who are treated with Afinitor[®] plus exemestane according to routine practice and the Summary of Product Characteristics or for whom treatment with Afinitor[®] and exemestane is indicated.
- Postmenopausal women with advanced hormone-receptor-positive, HER2/neunegative breast cancer without symptomatic visceral metastases.
- Recurrence or progression after a non-steroidal aromatase inhibitor (e.g. anastrozole, letrozole)
- ✓ Age ≥ 18 years
- Patients who were given information about this NIS and signed an informed consent form.

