There are no exclusion criteria except the contraindications listed in the Summary of Product Characteristics. Participating patients may not take part in any clinical study in parallel to this, as this does not constitute routine medical practice and is therefore counter to the aims of an NIS pursuant to Section 4 para. 23 sentence 3 AMG.

Notes on the indication for Afinitor[®] and exemestane and contraindications and possible side effects are provided in the enclosed Summary of Product Characteristics. Treatment may not be administered for the purpose of inclusion in the NIS, but must be given exclusively for the purpose medical and therapeutic need.

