8.2 Patient information and informed consent form

Every patient must be given information by the treating physician about the aims and the nature and scope of documentation before being included in the NIS. Because an authorised drug is being observed in the NIS, specific patient information that goes beyond the scope of the instructions for patients is not needed.

A patient may not be included in the NIS without her written consent to having her data documented in the NIS and to having her patient file viewed for comparing data. Processing of personal data for the purpose of comparing the data collected with the patient's medical record (SDV) is subject to EU Directive 95/46/EC and national data protection regulations.

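### Section 6.2 treats broad eligibility as proof of representative selection within sites, but nothing governs who is documented and the entry and analysis rules favour patients who stay on treatment

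*Protocol*

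**What the plan says.** Section 6.2 of the protocol gives one reason for one conclusion. No exclusion criteria are explicitly defined, meaning that "all patients who fulfil the requirements for documentation can actually be documented", and therefore "the representativeness of the selection within the sites is assured".

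Other sections determine who reaches the data:

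- Section 6.1 lets a patient enter after treatment has begun, within a limit: "exemestane was started a maximum of 6 weeks before they gave their consent to participate in this NIS". It sets a second condition for these late entrants, namely that "they are currently receiving Afinitor" (together with exemestane).
- Section 8.2 makes consent a condition: "A patient may not be included in the NIS without her written consent".
- Section 12.4 limits the analysis to patients with documented administration or prescription of Afinitor and at least one follow-up while on treatment.
- Section 6.6 describes one list of patients at the site. It links the numbers of documented patients to their identities for source data verification.

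No section asks sites to document eligible patients consecutively or completely, or to record eligible patients who were not documented.

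**The concern.** The argument in 6.2 moves from permission to outcome. Wide entry criteria define the pool from which patients may be taken; they do not determine which members of that pool are taken. For that, a rule of selection is needed, such as consecutive inclusion, and the protocol has none.

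The rules it does have are not neutral. A patient not consented before her first dose can enter only while still on treatment. If she stopped earlier because of progression or intolerance, she is lost to the study. The on-treatment follow-up requirement works in the same direction.

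This bears on the stated purpose. Section 4 says the data should show whether the efficacy seen in the approval study is replicated in routine care, and it notes that stomatitis often appears soon after treatment start. Losing early failures would tend to lengthen PFS and understate early toxicity. A reader who relies on 6.2 would have no reason to look for such a shift.

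**Working it through.** **The plan's own figure.** Section 6.2 gives 3000 patients as more than 11% of 24,000 to 26,000 eligible patients. 3000/26,000 = 11.5% and 3000/24,000 = 12.5%, so the figure is reproduced. It describes national coverage and says nothing about how patients are chosen within a site.

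**The inference.** The premise is that an eligible patient can be documented. The conclusion is that documented patients represent the eligible patients at the site. The link would have to be a rule that they all are documented, or that those who are form an unselected sample. Sections 6.1, 6.2, 6.6, 6.7 and 8.2 contain no such rule. The conclusion does not follow.

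**Direction of the two filters.** Late entry under 6.1 requires ongoing treatment at consent. Analysis under 12.4 requires a follow-up under treatment. Each removes patients who stop early, and neither removes patients who stay on.

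**Possible size of the 6-week window (illustration).**

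Inputs:
- Window: 6 weeks (6.1), w = 42/30.4375 = 1.38 months.
- True median PFS m: 7.8 months (6.3, local evaluation in the approval study), with 11.0 months (6.3, central evaluation) as a second value.
- Assumed: exponential PFS; PFS timed from treatment start; being progression-free stands in for being on treatment; a share f of documented patients enters exactly at 6 weeks and the rest at treatment start; no delayed-entry correction.
- The documents do not give f, so a range is shown.

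Hazard: λ = ln 2 / m. Share progressed by 6 weeks: 1 − exp(−λw).
- m = 7.8: λ = 0.0889, λw = 0.1226, share = 11.5% (its match with the coverage figure above is coincidence).
- m = 11.0: λ = 0.0630, λw = 0.0870, share = 8.3%.

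For t > w, the apparent curve is S(t) = (1 − f)·exp(−λt) + f·exp(−λ(t − w)). Setting S(t) = 0.5 gives:

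apparent median = m + ln[1 + f(exp(λw) − 1)] / λ

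| f | m = 7.8 | m = 11.0 |
|---|---|---|
| 0 | 7.8 | 11.0 |
| 0.25 | 8.16 | 11.36 |
| 0.50 | 8.51 | 11.70 |
| 1.00 | 9.18 | 12.38 |

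For example, with m = 7.8 and f = 0.5: exp(0.1226) − 1 = 0.1305; ln(1.0652) = 0.0632; 0.0632/0.0889 = 0.71; 7.8 + 0.71 = 8.51 months.

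Entry earlier than 6 weeks would shift the median less. The calculation leaves out patients who stop for intolerance, the filter in 12.4, and any choice by the physician.

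**The case against.** The strongest reply is that the study is openly descriptive (12.1), that it expressly wants patients the approval study left out (sections 4 and 6), and that event times are to be derived in the SAP (12.2), which may deal with late entry. All of this is fair. It limits the consequence, but it does not supply a selection rule and so does not support the word assured.

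Several stronger readings are tempting and should not be drawn:

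- *Sites pick patients at will, or wait to see who does well.* The protocol does not say this. It is silent on the order of inclusion, and entry time is bounded. The point is the missing rule, not a motive.
- *The premise of no exclusion criteria contradicts 6.1.* Section 6.1 says "There are no exclusion criteria except the contraindications listed in the Summary of Product Characteristics" and adds "Participating patients may not take part in any clinical study in parallel to this". The first follows from on-label use. The second is explained there: such treatment is not routine practice. Both define the target population, and 6.2 speaks only of patients who meet the requirements.
- *About 88% of eligible patients go unobserved.* The complement of 11.5–12.5% is 87.5–88.5%, but the base is a national pool for whom the combination is an option, not patients treated at the roughly 400 sites. The share documented within sites is not given.
- *Regional spread undermines the claim.* A nearly "equal regional distribution across the country" concerns the choice of sites, not selection within them, and there are no regional patient figures against which to test it.

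It can also be said that consecutive inclusion cannot remove selection by consent, and that on-site monitoring reaches only 5% of sites (6.8). Both are true, which is why the corrected sentence should state an aim rather than a guarantee.

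**Conclusion.** The sentence in 6.2 is wrong as written. Absence of exclusion criteria cannot assure representative selection within sites, nothing else in the protocol provides it, and the rules in 6.1 and 12.4 select towards patients who remain on treatment.

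The actual size cannot be determined from the documents. Under the assumptions shown, the 6-week window alone would add about 0.4 to 1.4 months to the apparent median PFS as the late-entrant share goes from 25% to 100%. It would add nothing if all patients entered at treatment start or if delayed entry were handled in the analysis. These figures show direction and possible size; they are not an estimate of bias in this study.

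A reader might infer that the results will be biased or the descriptive analyses invalid. The documents do not support that. The finding is that a guarantee is given without a basis, in a study whose purpose depends on it. No planned number changes.

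**What to change.** 1. Add to section 6.1 that sites offer documentation to eligible patients consecutively, in order of treatment start and preferably before the first dose. Section 6.1 already admits patients for whom the treatment is indicated, and section 6.4 wants quality of life and physical activity assessed before treatment begins, so earlier entry fits the plan. The instruction governs documentation only and leaves treatment decisions untouched.
2. In section 6.2, replace the claim of assurance with a statement that representative selection within sites is sought through consecutive inclusion but cannot be guaranteed.
3. Report the share of patients who entered after treatment start and the time from start to consent. Show PFS with delayed entry (left truncation), or without late entrants, as a sensitivity analysis. This addresses the entry window only; it does not correct for which patients were offered documentation.

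The cost is one instruction to sites, one reworded sentence and one additional analysis. Sites lose a little freedom, and the protocol makes a less favourable claim. An anonymous count of eligible patients not documented would allow the instruction to be checked, at the price of more site work; it is optional. If consecutive offering proves impracticable, items 2 and 3 still stand, with the reference to consecutive inclusion removed from item 2.

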6.3 Observation period

The approval study for Afinitor[®] demonstrated a statistically significant advantage of Afinitor[®] in combination with exemestane over placebo plus exemestane, consisting in a prolongation of PFS from 3.2 to 7.8 months according to the local radiology evaluation. The risk of progression of the cancer was reduced by 55%. These results were confirmed by an independent central radiology assessment (4.1 vs. 11.0 months, 62% reduction of risk). In order to obtain relevant results corresponding to the stated goals, the observation period corresponds with the duration of treatment with the combination of Afinitor[®] and exemestane, ending however no later than 31/12/2017 at the latest. The last patient will thus be observed for a maximum of 12 months. If the therapy with Afinitor[®] and exemestane is stopped prior to disease progression, the follow up period will be extended until time of progression / death of the patient. A patient who does not start the indicated treatment with Afinitor[®] and exemestane, for whatever reason, cannot be documented in the NIS. Treatment interruptions are documented over the entire treatment period. If treatment with Afinitor[®] and/or exemestane is discontinued permanently for whatever reason, the date of the last administration and the main reason for discontinuation are to be documented.

Timeline of the NIS:

Start of the observation phase:	October 2012
Inclusion of last patient in the documentation:	December 2016
End of the observation phase:	December 2017
Last data collection in the eCRF:	March 2018
Final report:	December 2018

Only data entered into the NIS database via web application by 31/03/2017 or questionnaires that were sent to the CRO **and and application** by 31/03/2018 can be used for the statistical analysis and will be eligible for remuneration (signature required).

6.4 Observation parameters

In this non-interventional study, diagnostic measures and medically indicated examinations are documented only if they were conducted in accordance with normal routine practice. The points described under 6.4.1 to 6.4.3 are guideline observation parameters and are solely for the purpose of orientation.

Optional intermediate examinations can be anticipated per patient corresponding to routine practice in normal conditions. Findings are to be documented at the time of inclusion and after approx. 2 weeks, 1, 3, 6, 9, 12... etc. months until the end of treatment with Afinitor[®] and exemestane or until the end of the observation phase, whichever occurs first.

To assess quality of life and physical activity before the start of treatment and during treatment, questionnaires in hard copy will be provided. To estimate patient compliance, patients will be given calendar overviews.

6.4.1 Observation parameters at the initial examination

Prerequisite: written consent form for participation in the study

- Date of start of observation/initial examination
- Patient history, demographic data, and characteristics of the disease
 - Date and characteristics of the initial diagnosis (month/year, tumour stage (TNM), grading, histological subtype, Ki67)
 - Diagnosis-specific history at the first evidence of metastasis (date, type of metastasis, location)
 - Previous and current treatment (radiotherapy, pharmacological treatment with start, end, and best result observed with respect to tumour response)
 - Details of previous tumour resection and metastases and their tumour biology if available
- ECOG performance status if conducted
- Height, weight
- Current tumour status (TNM stage, location of metastases and latest imaging (CT, MRI, ultrasound, bone scintigraphy, etc.))
- Reason for switching to Afinitor[®] (progression, patient wish, not progression-induced switch)
- Comorbidity
- Antiresorptive treatment to prevent bone-related complications if bone metastases are present
- Planned prophylactic measures against stomatitis
- Quality of life: patient questionnaire EORTC QLQ-C30/BR23
- Physical activity: "Godin Leisure-Time Exercise Questionnaire" and "Physical Activity Scale" (PAS)
- Compliance: calendar overview provided to estimate treatment compliance
- Prescription for Afinitor[®] (date, dosage, pack size)
- Planned follow-up visit

6.4.2 Observation parameters two weeks after the start of documentation (prospectively after implementation of Amendment 2 in the eCRF)

If a visit takes place approx. 2 weeks after the start of documentation in accordance with routine practice, the following observation parameters are documented at this time:

- Date of follow-up
- Documentation of stomatitis treatment if any was needed and given
- Current tumour treatment with Afinitor[®] (dosage, dose reduction, treatment breaks, reason for dose adjustment)
- Patient questionnaire on stomatitis prophylaxis
- Documentation of adverse events
- Next scheduled follow-up

6.4.3 Observation parameters at later follow-ups

In accordance with routine practice, documentation of the following observation parameters is to be made at regular follow-up s (e.g. after 1 month, 3 months and thereafter at 3-month intervals):

- Date of follow-up
- ECOG performance status if conducted
- Weight
- Imaging follow-up (not at month 1)
- Evaluation of response to treatment (from imaging and/or clinical assessment of status in accordance with routine practice)
- Current tumour treatment with Afinitor[®] (dosage, dose reduction, treatment breaks, reason for dose adjustment)
- Prophylactic measures relating to treatment management
- Quality of life: EORTC QLQ-C30/BR23 patient questionnaire
- Physical activity: "Godin Leisure-Time Exercise Questionnaire" and "Physical Activity Scale" (PAS)
- Compliance based on a calendar overview, if available
- Documentation of adverse events
- Documentation of stomatitis treatment if any was necessary and given
- Patient questionnaire on stomatitis prophylaxis
- Prescription for Afinitor[®] (date, dosage, pack size)
- Next scheduled follow-up

6.4.4 End of observation

The documentation of the end of treatment with Afinitor[®] is not bound to the target observation interval (e.g. after month 1, 3, 6 etc.), but should be carried out at the soonest possible time that is

in line with medical practice. The following observation parameters will be recorded:

- Reasons for the end of documentation (withdrawal of consent, lost to follow-up, death, discontinuation of treatment with Afinitor[®])
- Date, dosage and pharmaceutical form of the last administration of Afinitor®
- Reason for ending treatment (lack of efficacy, disease progression, intolerability, poor compliance)
- Evaluation of response to treatment (from imaging and/or clinical assessment of status in accordance with routine practice)
- Follow-up treatment
- Documentation of adverse events

6.4.5. PFS Follow Up

- Date of progression or death as well as type of follow up treatment, if therapy with Afinitor[®] an exemestane has been stopped prior to disease progression
- Documentation of AEs and SAEs with causal connection to Afinitor[®] an exemestane and occurrence of death, independent from causal connection

6.5 Drugs

Afinitor[®] is an oral inhibitor of the *mammalian target of rapamycin* (mTOR). Afinitor[®] is approved in combination with exemestane for the treatment of postmenopausal patients with advanced HR-positive, HER2/neu-negative breast cancer with no symptomatic visceral metastases, after a recurrence or progression following an NSAI. Afinitor[®] is available as 10 mg, 5 mg and 2.5 mg tablets to facilitate any necessary dose reductions.

Exemestane belongs to the group of aromatase inhibitors and prevents the synthesis of oestrogens by irreversible binding to the aromatase enzyme. The active ingredient is indicated for the treatment of advanced breast cancer in women after natural or induced menopause following progression under anti-oestrogen treatment.

Afinitor[®] and exemestane are administered according to current routine practice and the recommendations of the respective Summary of Product Characteristics, based exclusively on medical and therapeutic need. The patients are treated with commercially available products. Information on dosage, warnings, precautionary measures, combination treatment and compatibility with other medication is provided in the accompanying Summary of Product Characteristics.

Dose adjustment due to toxicity

If serious and/or unacceptable side effects with a suspected correlation to Afinitor[®] occur, the dosage can be adjusted according to the Summary of Product Characteristics.

6.6 Study documentation

The study documents include

- Agreement to participate (two original documents: please send one copy to the CRO , the other copy is for your records)
- Patient information and informed consent form (two original documents: one copy is for the study doctor, the other one is fpr the patient. Please note: the written informed consent form must be archived by yourself)
- This observation plan
- Patient questionnaires (one questionnaire on quality of life, two questionnaires on physical activity, one questionnaire on stomatitis prophylaxis)
- The diary documenting medication intake
- A documentation guideline.

The Summaries of Product Characteristics for Afinitor[®] and exemestane are included. In addition, the physician is given a brochure for patients with suggestions and information on "physical activity with advanced breast cancer". To support exercise, the physician can also give patient a pedometer with which they can observe their own activity on a voluntary basis.

All documentation in the database is labelled with the acronym of the NIS and a unique sequential patient number consisting of the site number, and a patient number assigned in ascending order (e.g. for site 100 with 5 patients: patient 100/01 to patient 100/05). In order to identify a patient for a potential comparison of the data collected with the patient record (source data verification – SDV) the participating physician must keep a separate identification list that makes it possible to link the number of a specific patient to her name, date of birth, and age internally within the practice. The identification list is intended to be retained exclusively by the participating physician. It must be ensured that the number on the patient questionnaires on quality of life and physical activity correspond with the patient number in the database. These questionnaires are to be completed by the patients themselves.

